**List of abbreviations**

AASLD	American Association for the Study of Liver Diseases
AE	Adverse event
ALT	Alanine aminotransferase
ANC	Absoulte neutrophil count
AR	Acute rejection
AST	Aspartate aminotransferase
AUROC	Area Under Receiver Operating Characteristic (Curve)
CFSE	Carboxyfluorescein succinimidyl ester
CKD	Chronic kidney disease
CNI	Calcineurin inhibitor
CBC	Complete blood count
Cr	Creatinine
CRF	Case Report/Record Form
CRD	Clinical Research and Development
CPO	Country Pharma Organization
CRO	Contract Research Organization
CSR	Clinical Study Report
CTC	Comprehensive Transplant Center
DR	Donor
DSA	Donor specific antibodies
DSMB	Data Safety Monitoring Board
ECG	Electrocardiogram
eCRF	Electronic case report form
eGFR	Estimated glomerular filtration rate
EVL	Everolimus
FDA	Food and Drug Administration
GCP	Good Clinical Practice
GFR	Glomerular filtration rate
GGT	Gamma-Glutamyl Transpeptidase
HBV	Hepatitis B virus
HCV	Hepatitis C virus

HCV-R	Hepatitis C virus recurrence
HgbA1C	Hemoglobin A1C
HIPAA	Health Insurance Portability and Accountability Act
HIV	Human Immunodeficiency Virus
HLA	Human leukocyte antigen
HLA-DR	Human leukocyte antigen-donor
ICH	International Conference on Harmonization of Technical Requirements for Registration of Pharmaceuticals for Human Use
ICH	International Conference on Harmonization
I/E	Inclusion/exclusion
ICH	Immunohistochemical
IL-2	Interleukin 2
IM	Immune Monitoring
IMS	Immune Monitoring Signals
IRB	Institutional Review Board
IS	Immunosuppression
IVRS	Interactive Voice Response System
LFT	Liver function tests
LT	Liver transplantation
MAP	Multi-Analyte Profiling
MFI	Mean Fluorescence Intensity
miRNA	Micro ribonucleic acid
MLR	Mixed lymphocyte reaction
MPA	Mycophenolic acid
mRNA	Messenger ribonucleic acid
NK cells	Natural killer cells
NU	Northwestern University
NU IRB	Northwestern University Institutional Review Board
OLT	Orthotopic Liver Transplant
PBMC	Peripheral blood mononuclear cell
PHI	Protected health information
PI	Principal Investigator

PTLD	Post-transplant lymphoproliferative disorder
PRED	Prednisone
RM-ANOVA	Repeated Measures of Analysis of Variance
RN	Registered nurse
SAE	serious adverse event
SOC	Standard of Care
SRL	Sirolimus
SI	Stimulation indices
TAC	Tacrolimus
TAC-WD	Tacrolimus withdrawal
Tregs	T-regulatory cells
WBC	White blood cell

## Glossary of terms

Assessment	A procedure used to generate data required by the study
Control drug	A study drug used as a comparator to reduce assessment bias, preserve blinding of investigational drug, assess internal study validity, and/or evaluate comparative effects of the investigational drug
Enrollment	Point/time of patient entry into the study; the point at which informed consent must be obtained (i.e. prior to starting any of the procedures described in the protocol)
Investigational drug	The study drug whose properties are being tested in the study; this definition is consistent with US CFR 21 Section 312.3 and is synonymous with "investigational new drug."
Medication number	A unique identifier on the label of each medication package in studies that dispense medication using an IVR system
Patient number	A number assigned to each patient who enrolls in the study. When combined with the center number, a unique identifier is created for each patient in the study.
Stage	A major subdivision of the study timeline; begins and ends with major study milestones such as enrollment, randomization, completion of treatment, etc.
Period	A minor subdivision of the study timeline; divides phases into smaller functional segments such as screening, baseline, titration, washout, etc.
Premature patient withdrawal	Point/time when the patient exits from the study prior to the planned completion of all study drug administration and assessments; at this time all study drug administration is discontinued and no further assessments are planned
Randomization number	A unique identifier assigned to each randomized patient, corresponding to a specific treatment arm assignment
Stop study participation	Point/time at which the patient came in for a final evaluation visit or when study drug was discontinued whichever is later
Study drug	Any drug administered to the patient as part of the required study procedures; includes investigational drug and any control drugs
Study drug discontinuation	Point/time when patient permanently stops taking study drug for any reason; may or may not also be the point/time of premature patient withdrawal
Variable	Information used in the data analysis; derived directly or indirectly from data collected using specified assessments at specified time points

## Protocol synopsis

**Title of study:** Biomarkers Predicting Successful Tacrolimus Withdrawal and Everolimus (Zortress®) Monotherapy Early After Liver Transplantation

**Purpose and rationale:**

The purpose of this study is to develop a biomarker strategy testing transplant immunoregulation to guide safe elimination of calcineurin inhibitor (CNI) therapy in favor of everolimus (EVL) early after liver transplantation (LT). We plan to analyze a set of biomarkers testing genomic and immunophenotypic measures of immune reactivity and regulation, expected to be enhanced by EVL and predictive of successful conversion.

**Objectives:**

**To identify cellular and genomic metrics of immune regulation that may predict successful TAC withdrawal in favor of EVL early after LT.**

Our *overall objective* is to utilize biomarkers that will clarify the decision to consider tacrolimus withdrawal/EVL (TAC-WD/EVL) and maintain EVL without TAC. Proving the hypothesis that EVL promotes early immunoregulation in those patients not developing rejection with TAC-WD would provide:

- 1) rationale for early CNI to EVL conversion when the benefit and risk are highest
- 2) bioassays to guide selection of appropriate candidates for TAC-WD/EVL vs. continued TAC in patients likely to develop rejection with CNI withdrawal.

**Primary endpoint:**

The primary endpoint is the peripheral blood Treg% (or other immunoregulatory cells) and messenger ribonucleic acid (mRNA) acute rejection (AR) signatures seen prior to and during either successful (no rejection) vs. failed (rejection) TAC-WD/EVL.

**Secondary endpoints:**

Clinical endpoints as correlates for the success and failure of TAC-WD/EVL will serve as secondary endpoints. This will include but not be limited to the following at 6 months ( $\pm$  1 month) post-LT: liver allograft and renal function, EVL & TAC side effects, infectious/malignant complications, and patient/graft survival. At study end, all secondary endpoints will be statistically compared between those who succeed or fail TAC-WD/EVL.

**Population:**

We will select adult ( $\geq$  18 yrs. of age) LT recipients without immune disease, active viral disease, and previous or combined organ transplantation to avoid the confounding of coexistent inflammatory/infectious processes and prior transplants on the biomarker analysis.

**Inclusion/Exclusion criteria:**

**Inclusion Criteria:**

- Adult LT candidates  $\geq$  18 years of age
- Listed for or recent (within 2 months) recipient of deceased or living donor liver transplantation

**Exclusion Criteria:**

- Combined or previous organ transplantation
- Human immunodeficiency virus (HIV) infection
- Inability to provide informed consent or comply with the protocol.
- Transplantation for autoimmune liver disease (Autoimmune hepatitis, Primary Biliary Cirrhosis, Primary Sclerosing Cholangitis)

**Investigational and reference therapy:**

Zortress® (everolimus) at advised doses and trough levels.

**Study design:**

Overall: Prospective, open-label pilot study comparing immunoregulatory assays in non-viremic LT patients undergoing TAC-WD/EVL. The patients will serve as their own control for assays, clinical, biochemical, and histological measures, and the groups will be divided and compared by the presence or absence of rejection before, during and after the TAC-WD/EVL phase (months 0-6 ( $\pm$  1 month)). As this is a pilot study, we hope to generate these preliminary data to power a larger trial testing the specific biomarker(s) at more specific time-points identified here in more definitively determining who may or may not be successful with undergoing CNI withdrawal in favor of EVL.

**Efficacy assessments:**

- The proportion of patients who are successfully withdrawn from TAC and continued on EVL without rejection or other complications at six months ( $\pm$  1 month) post-LT.
- The following assessments following addition of EVL at one to two months and attempted withdrawal of TAC between 3-6 months ( $\pm$  1 month) in favor of EVL maintenance: liver allograft and renal function, EVL & TAC side effects and discontinuations, infectious/malignant complications, and patient/graft survival.

- Biomarker assessments: Peripheral blood Treg% (or other immunoregulatory cells) and messenger ribonucleic acid (mRNA) AR signatures seen prior to and during either successful (no rejection) vs. failed (rejection) TAC-WD/EVL.

**Other assessments:**

- Other samples collected for future studies (see exploratory objectives below)

**Data analysis:**

The primary objective is to test the working hypothesis that, in a prospective study, cellular and genomic markers of immunoregulation become more pronounced after early rejection-free TAC-WD/EVL compared to failed (rejection) TAC-WD. Conversely, if these markers do not signify immunoregulation, we hypothesize that TAC-WD/EVL will not be successful (i.e. rejection will ensue requiring reinstatement of TAC). Our hypothesis is based on our previous observations that late mTOR-I conversion increased % of Treg/DCreg in blood/tissue sites and generated immunoregulatory proteogenomic signatures and that AR can be diagnosed in the peripheral blood by genomic microarrays. Therefore, the plan is to perform sequential flow cytometry immunophenotyping and genomic signature analysis in the blood before, during and after attempted TAC-WD/EVL.

**Studies Planned and Methods:**

i) Blood Immunophenotyping. The approach will be to conduct flow cytometry immunophenotyping of peripheral blood before TAC-WD initiation (3 months ( $\pm$  1 month)), right at total TAC-WD (4 months ( $\pm$  1 month)), 2 weeks after full TAC-WD (4.5 months ( $\pm$  1 month)) and study end (6 months ( $\pm$  1 month)) post-LT to analyze cellular changes. Methods: The Immune Monitoring Laboratory at NU will perform the PBMC immunophenotyping. For statistical analysis, we perform within subject comparisons on PBMC for both successful and failed TAC-WD/EVL groups using appropriate paired analysis (paired t-test or Wilcoxon Signed Rank test). For the main hypothesis testing, repeated measures of analysis of variance (RM-ANOVA) are used to test the trajectory variations between the groups on PBMC over time. Two-sided F-test statistics are applied;  $\alpha=0.05$  (stats by NU Transplant Statistician).

ii) Gene Expression Microarrays: The approach will be to conduct parallel serial genomic bioassays of peripheral blood before and after attempted TAC-WD/EVL (same time points as immunophenotyping). Methods: The Genomics Core at Scripps will perform the microarray analysis. Blood will be collected in PaxGene tubes and sent to Scripps for the gene microarrays. For statistical analysis, we report for each mRNA and microRNA comparison the T-test p-value, its non-parametric analog (Kruskal Wallis test), the fold change, and for multi-analyte signatures, the area under the receiver operating curve (concordance index/C-index) and q-values by member genes/proteins. We then calculate the predictive accuracy, sensitivity and specificity of each signature (statistics by [name] informatics group at Scripps Clinic)

## 1 Background

It has been assumed that standard IS agents, the calcineurin inhibitors (CNI) cyclosporine and tacrolimus (TAC), are indefinitely required to prevent allograft rejection following liver transplantation (LT). However, this has occurred at the expense of chronic CNI toxicity, e.g. chronic kidney disease (CKD), metabolic complications, infections and malignancy. The mortality related to CKD is only remediated by a curative kidney transplant, usurping costs and valuable organ resources. While CNI therapy is universally given immediately after LT, subsequent conversion from CNI to non-CNI therapy could reduce these adverse effects. Agents such as mammalian target of rapamycin inhibitors (mTOR-I) sirolimus (SRL) and everolimus (EVL) have a different mechanism of action and may stabilize or improve renal function in patients with CKD related to CNI therapy. However, most of the studies have involved late CNI to mTOR-I conversion when CKD is already “set in” and likely irreversible. Thus, early full conversion (<1 year post-op), i.e. CNI discontinuation in favor of mTOR-I therapy) before the onset of irreversible CKD, would be the most optimal approach. However, higher SRL doses and troughs ( $\geq 8$  ng/mL) are required in this time period given the lower immunosuppressive potency of SRL vs. CNI, but this can result in intolerable SRL side effects and discontinuation in ~30% and still lead to rejection. In addition, SRL has known risks of hepatic artery thrombosis in the early post-operative period and cause mortality in liver recipients, thus leading to a “black box warning” and lack of indication in this population. Taking these considerations into account, safer, more tolerable mTOR-I therapy (such as EVL) would be preferable for use in the LT population.

Nevertheless, faced with CKD progression, clinicians are commonly confronted with difficult decisions, none of which are clearly considered the most optimal: 1) maintain CNI therapy and accept the nephrotoxicity; 2) reduce CNI to sub-therapeutic levels and risk acute rejection; 3) reduce CNI doses and add other IS (mycophenolic acid or mTOR-I) to decrease the rejection risk, but accept the potential for CKD progression given the continued CNI therapy and the combined toxicity/immunosuppression of the second agent; 4) stop CNI and convert to a non-nephrotoxic agent (mTOR-I like EVL) to minimize CNI effects and over-immunosuppression. While some studies have not shown an increased risk of rejection with the last approach, a recent major randomized trial did demonstrate a higher risk compared to either TAC monotherapy or combination low dose TAC and EVL. Despite this arm (TAC-withdrawal and continued EVL; TAC-WD/EVL) being stopped early because of this, the remaining patients had the most preserved glomerular filtration rate (GFR) at one-year post-LT. Thus, it would represent a major advance to be able to determine more specifically which patients would fare well (improved GFR without AR) or poorly (rejection) with early TAC-WD/EVL. However, the absence of serial, specific biomarkers of immunoregulation available to guide this approach is a significant roadblock to achieving this endpoint.

Therefore, specific to this proposal and supported by our unique data in LT recipients, an unexplored advantage of mTOR-I therapy lies in its potential to promote an immunoregulatory state. This could facilitate success with early CNI withdrawal in favor of EVL under current target doses/trough levels. As the most immunoregulatory organ transplanted, the liver houses numerous extramedullary immunoregulatory hematopoietic cells and secretes several immunoregulatory proteins. The percentage of LT recipients able to undergo IS withdrawal directly from CNI therapy appears to be the highest of all organ recipients, although still only ~20% successful. This clinically unacceptable rate may be due to CNI mechanisms inhibiting immunoregulation and the lack of predictive assays to detect immunoregulation. A key difference between mTOR-I and CNIs is their effect on regulatory T cells (Tregs) important in the suppression of alloimmunity. As an inhibitor of downstream IL-2 signaling after T cell activation, mTOR-I blocks alloreactive T cell proliferation but appears to promote Tregs (CD4+CD25highFOXP3+), regulatory cytokines (TGF- $\beta$ 1), and tolerogenic dendritic cells (DC2, ILT3+/4+). In contrast, CNI therapy inhibits IL-2 transcription and has been thought to negatively impact Treg generation.

We have also uniquely demonstrated robust donor-specific regulatory effects of SRL in MLR cultures. In these studies, TAC, SRL or media without agents were added separately to MLRs using HLA 2 DR matched and mismatched volunteers. Stimulation indices (SI) of H-TDR uptake, cell proliferation, and the generation of carboxyfluoroscein succinimidyl ester (CFSE) labeled CD4+CD25HighFOXP3+ cells by flow cytometry were initially compared. Each group of MLR-generated cells were then added as third components to CFSE labeled responding cells in freshly prepared primary MLRs, to determine allo-specific vs. non-specific inhibitory and Treg “recruitment” effects (*in vitro* “infectious tolerance”). Tacrolimus inhibited SI and CD4+CD25HighFOXP3+ cell generation in both HLA-DR matched and mismatched pairs, particularly at therapeutic levels ( $\geq 5$  ng/ml). SRL had an equivalent lymphoproliferative inhibitory effect in matched pairs but was associated with a significantly higher % generation of CD4+CD25HighFOXP3+ cells. SRL-MLR-generated Tregs added as third components allo-specifically inhibited MLR proliferation and “recruited” additional autologous Tregs compared with addition of TAC- or media-MLR-generated cell preps [Fig. 1, ref]. These results can explain the differing *in vitro* effects of these agents, now with donor-specific regulatory implications for mTOR-I. The immunoregulatory effects of EVL appear to be even more profound than SRL. In a Novartis supported laboratory study (submitted to the American Transplant Congress; manuscript in preparation), we analyzed and compared the *in vitro* immunoregulatory effects of EVL vs. SRL vs. TAC and found the greatest augmentation of Tregs with EVL in culture, particularly in combination with mycophenolate.

Clinically, we demonstrated in another study that LT recipients previously converted to SRL had higher percentages of PBMC Tregs compared to recipients on other IS therapies. This led to a prospective TAC to SRL conversion trial supported by the American Association for the Study of Liver Disease Career Development Award and Wyeth/Pfizer ([name]). Our aim was to determine if systemic phenotypic Tregs (CD4+CD25highFOXP3+), regulatory dendritic cells (DCregs: ILT3+/4+), and immunoregulatory proteogenomic signatures increase in LT recipients converted directly from TAC to SRL monotherapy. Twenty non-immune non-viremic LT recipients were successfully converted for renal dysfunction. The mean eGFR increased from 45.9±7.9 to 49.6±10.8 (p=0.003). Tregs increased significantly in PBMC, marrow [Fig. 2, from ref] and LT biopsy cultures. Biopsy immunohistology FOXP3:CD3 and CD4:CD8 ratios became significantly higher after conversion [Fig. 3, from ref]. Peripheral blood DCregs increased significantly (Fig. 2, p<0.01). Both pre- (TAC) and post- (SRL) conversion sera inhibited MLR proliferation, although only TAC sera suppressed Treg generation. 289 genes and 22 proteins, many of which are important in immunoregulatory pathways, were newly expressed after conversion [Fig. 4: from ref]. In conclusion, these studies demonstrated that TAC to SRL conversion increases systemic (blood, allograft, marrow) Tregs, blood DCregs and regulatory proteogenomic signatures in LT recipients. However, it is not known if this profile correlates with and predicts successful *early* mTOR-I use (i.e. TAC-WD/EVL) as in this proposal.

Equally important as the chosen IS regimen is identifying predictive biomarkers, such as those we have tested above. Various reports demonstrate a higher percentage of CD4+CD25highFOXP3+ cells, DC2,  $\gamma\delta$  T cells and specific genomic signatures in tolerant LT recipients versus those on maintenance IS. Our collaborative group has previously performed proteogenomic assays (mRNA profiles, proteomic analytes) to identify markers of acute rejection (AR) and chronic allograft nephropathy in kidney recipients, as well as CKD post-LT. In addition, we recently conducted a study profiling (mRNA gene expression) 114 blood and 57 liver biopsy samples of patients with different clinical phenotypes, and have identified both blood and tissue mRNA signatures that can distinguish AR from other major causes of graft injury (hepatitis C recurrence, mixed HCV-R and AR, other causes) in LT recipients with high predictive accuracy (AUC 0.89 – 0.9; Figure 5). These biomarkers have the potential to be useful to enhance the specificity of diagnosis, particularly in managing patients with contrasting etiologies (e.g., AR vs. HCV-R). In addition, the immune/inflammatory nature of these AR profiles may help inform decisions to perform liver biopsies and in immune monitoring during immunosuppression reduction, as proposed herein. Yet, the presence of ‘snap-shot’ non-specific cell populations and differential gene/protein arrays only provides circumstantial evidence for their role in immunoregulation. Prospective sequential assays would provide a more accurate measure of the effects of mTOR-I on immunoregulation. We anticipate that these expression patterns will be useful as regulatory signatures that may predict successful CNI withdrawal, as suggested by our recent trial and other reports.

## 2 Purpose and rationale

We propose to develop a biomarker strategy testing transplant immunoregulation to guide safe elimination of CNI therapy in favor of EVL early after LT. We plan to analyze a set of biomarkers testing genomic and immunophenotypic measures of immune reactivity and regulation, expected to be enhanced by EVL and predictive of successful conversion. These bioassays will be compared in this initial pilot study prospectively between non-viremic LT recipients on TAC + EVL combination therapy (EVL added at 1 to 2 months) who are either successfully (no rejection) or unsuccessfully (rejection) withdrawn from TAC at month 3-4 ( $\pm$  1 month) from LT. Our overall objective is to utilize biomarkers that will clarify the decision to consider TAC-WD/EVL and maintain EVL without TAC. Proving the hypothesis that EVL promotes early immunoregulation in those patients not developing rejection with TAC-WD would provide 1) rationale for early CNI to EVL conversion when the benefit and risk are highest and 2) bioassays to guide selection of appropriate candidates for TAC-WD/EVL vs. continued TAC in patients likely to develop rejection with CNI withdrawal.

## 3 Objectives

**Primary Objective:** To identify cellular and genomic metrics of immune regulation that may predict successful TAC withdrawal in favor of EVL early after LT.

*It is our hypothesis that these markers of immunoregulation are more pronounced with successful (no rejection) vs. unsuccessful (rejection) TAC-WD/EVL.* The approach will be to analyze the peripheral blood for phenotypic Tregs correlating with mRNA footprints of regulation. These analyses will be performed in a prospective pilot clinical trial of LT recipients on standard combination TAC and EVL at 1 to 2 months post-LT selected to undergo TAC-WD/continued EVL at 3-4 months ( $\pm$  1 month). Thus, based on the clinical trials, we expect rejection to occur in 20% in the 1-2 month period following TAC-WD/EVL and that this will be predicted by bioassays analyzed prior to and/or immediately after full TAC-WD. Alternatively, we expect 80% to not experience rejection with TAC-WD/EVL and that this will be predicted by bioassays analyzed prior to and/or right after full TAC-WD. Therefore, the use of these assays would eventually serve to detect and predict appropriate candidates for successful early TAC-WD/EVL, enhancing the use of EVL in LT and allowing patients to be spared of CNI toxicity past the first 3-4 months following LT.

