### Criteria for Study Continuation and EVL addition (1 to 2 months post-LT):

1. Currently on TAC + prednisone +/- MPA therapy with no contraindication to starting EVL (i.e. wound infection; significant proteinuria (urine prot/cr ratio  $\geq 1.0$ ), hepatic artery thrombosis/stenosis, cytopenias (WBC  $< 1.5$ , ANC  $< 1.0$ , Platelet  $< 30$ , Hemoglobin  $< 7$ ), other deemed by investigator)
2. No more than 2 rejection episodes or 1 steroid-resistant rejection requiring lymphodepletion therapy
3. No active biliary, infectious, or malignant process
4. eGFR  $\geq 30$  ml/min/1.73m^2
5. No significant liver function abnormalities (Direct bilirubin, AST/ALT, Alkphos  $\geq 2x$  elevated)
6. If on current or prior antiviral therapy, HBV and HCV viral load should be undetectable
7. No combined transplantation (e.g. should be primary liver transplant alone)

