## 7 Visit schedule and assessments

**Table 7-1 Assessment schedule**

Visit**	1	2	3	4	5	6	7	At rejection***	Early Term./Study Comp.
Day	-90 to 0 +30 (Tx)	0	30	90	120	135	180		
Inc./Exc. Criteria	X		X	X	X				
Obtain informed consent	X								
Physical Exam			X	X	X		X		
Donor/Recipient Collections		X*							
Blood (Flow, PBMC, RNA, sera)			X*	X	X	X	X	X	
Tissue RNA								X	
Study Completion Form						X	X		X

\*unfunded and not mandatory for this protocol

\*\*  $\pm$  1 month window allowable

Visit 1 = Patient enrollment SOC visit (I/E criteria, informed consent)

Visit 2= Transplant SOC- if possible, donor spleen/lymph nodes and recipient lymph node/blood

Visit 3= Day 30 SOC visit- if Inc./Exc. criteria met, add everolimus and stop MPA if being used. Collect blood if possible (unfunded for this study).

Visit 4= Day 90 SOC visit- if Inc./Exc. criteria met, start tacrolimus withdrawal. Collect blood.

Visit 5= Day 120 SOC visit- if Inc./Exc. criteria met, stop tacrolimus. Collect blood.

Visit 6 = Day 135 visit- collect blood.

Visit 7= Day 180 SOC visit- Study termination. Collect blood.

\*\*\*At any biopsy concerning for rejection: Collect blood and tissue in RNAlater. If rejection, study termination.

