## **7.3 Efficacy**

The major efficacy assessment is the percentage of patients successfully withdrawn from TAC therapy in favor of EVL therapy without rejection or major complications. Rejection will be evaluated by liver biopsy when indicated (typically 2-3 fold increase in liver aminotransferases). If rejection occurs during any point of the trial following EVL addition, the study will be terminated for that patient.

Other efficacy endpoints will be the improvement in TAC side effects (renal, neurologic, metabolic, etc.) and development of EVL side effects (hyperlipidemia, edema, proteinuria, etc) in those successfully withdrawn from TAC without rejection. For those unable to withdraw from TAC due to rejection, we will assess for TAC side effects and EVL side effects if this drug is continued following rejection. Liver and renal function, and hematological parameters will be followed per SOC throughout this biomarker study

The PI and research coordinator will perform these assessments at the study time points at Northwestern and at any intervening time point if the patient needs a liver biopsy to exclude rejection or other complication (hospitalization, infection, etc.). Patients enrolled also will be contacted by phone for any changes in their immunosuppression dosing or other medications in between visits.

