#### **7.4.4 Laboratory evaluations**

At liver transplant donor/recipient collection of lymph nodes and liver biopsy tissue will take place if the patient is consented prior to transplantation. Liver biopsy tissue will also be collected at the time of a suspected rejection.

Blood samples for flow cytometry, PBMCs, RNA and sera will be collected at visits 3, 4, 5, 6, 7 and rejection.

Standard SOC laboratory tests will be performed per our transplant center post-LT protocol: CBC, CMP, trough IS levels three times weekly (0-1 month post-LT), two times weekly (1-3 months post-LT), one time weekly (3-6 months post-LT).

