### **10.2 Analysis of the primary objective(s)**

Primary objective: To identify cellular and molecular metrics of immune regulation that may predict successful TAC withdrawal in favor of EVL early after LT.

Overall Strategy and Rationale: The objective is to test the working hypothesis that, in a prospective study, cellular and genomic markers of immunoregulation become more pronounced after early rejection-free TAC-WD/EVL compared to failed (rejection) TAC-WD. Conversely, if these markers do not signify immunoregulation, we hypothesize that TAC-WD/EVL will not be successful (i.e. rejection will ensue requiring reinstatement of TAC). The rationale is that the immunoregulatory mechanisms of IS therapy (EVL vs. CNI) can be more adequately clarified and that a higher % of patients can undergo successful TAC-WD/EVL by utilizing these serial, safe blood biomarkers to predict rejection, before it occurs, i.e. by comparing these signals right before and after TAC-WD. Our hypothesis is based on our previous observations that late mTOR-I conversion increased % of Treg/DCreg in blood/tissue sites and generated immunoregulatory proteogenomic signatures and that AR can be diagnosed in the peripheral blood by genomic microarrays. Therefore, the plan is to perform sequential flow cytometry immunophenotyping and genomic signature analysis in the blood before, during and after attempted TAC-WD/EVL.

Studies Planned and Methods:

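### The blood sample after full tacrolimus withdrawal (Visit 6) counts as predictive whatever the liver enzymes show, so a marker that only follows visible graft injury could look predictive there

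*Combined protocol and SAP*

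**What the plan says.** Section 3 expects about 20% of patients to reject in the one to two months after withdrawal and states that "this will be predicted by bioassays analyzed prior to and/or immediately after full TAC-WD". Section 10.2 gives the same aim: "to predict rejection, before it occurs, i.e. by comparing these signals right before and after TAC-WD".

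Table 7-1 treats the visits differently:

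- **Visits 4 and 5.** Inclusion/exclusion criteria are checked at both. The Visit 5 entry reads "Visit 5= Day 120 SOC visit- if Inc./Exc. criteria met, stop tacrolimus. Collect blood". Item 5 of the continuation criteria under Section 5.2 begins "No significant liver function abnormalities (Direct bilirubin, AST/ALT, Alkphos" and sets the bound at a two-fold elevation. The month-3 criteria carry it forward.
- **Visit 6.** The whole entry is "Visit 6 = Day 135 visit- collect blood". No criteria check is marked. The stable-enzyme condition in Section 4 governs steps of the taper, so it does not reach this visit.

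Enzymes are followed throughout and lead to the outcome. Section 7.3 says "Rejection will be evaluated by liver biopsy when indicated (typically 2-3 fold increase in liver aminotransferases". Section 7.4.4 puts standard laboratory tests at once a week in months 3-6, while Section 4 says every 1-2 weeks. Section 7.4 says research blood is taken with the standard-of-care blood tests.

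The analyses in Section 10.2, repeated in 10.3.3, are paired tests, repeated-measures ANOVA between outcome groups, t-test and Kruskal-Wallis per transcript, and AUC, sensitivity and specificity per signature. None uses enzymes as a restriction, covariate or comparator, and none reports time from draw to biopsy. Section 10.2.4 lists no supportive analysis. Liver function is compared between groups only as a secondary clinical endpoint at month 6.

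**The concern.** A patient whose aminotransferases are already rising at Visit 6, but who has not yet been biopsied, is analysed as a future rejecter with a predictive sample. Any marker that moves with injury or with rejection under way will separate that patient from the non-rejecters. The separation is real, but it tells the clinician little that the enzyme result does not.

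This matters because the pilot exists to choose. Under Section 3.3, markers and time points that look predictive go into a larger study in which they would guide whether TAC is withdrawn or resumed. The weakness affects mainly the post-withdrawal sample, so it favours that time point over the pre-withdrawal ones. One of the two primary variables is an mRNA acute-rejection signature. Section 1 describes the group's earlier signatures as distinguishing existing rejection from other graft injury, so a marker of concurrent rejection is a realistic candidate.

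**Working it through.** **1. The plan's own figure.** Section 10.4 expects 20 patients to enter withdrawal, with 4-5 rejections and 14-15 without. 20 × 25% = 5 against 15, which matches the Figure 6 footnote. 20 × 20%, the rate in Section 3, gives 4 against 16. Both splits are used below. The plan states no power, effect size or SD.

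**2. One affected draw.** Assume every failure has a Visit 6 sample, and the marker rises 2 SD only in failures with raised enzymes and carries no signal otherwise. With a share f of failures affected:

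AUC = 0.5 + f × (Φ(2/√2) − 0.5), where Φ(1.414) = 0.921.

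- One of 5: 0.5 + 0.20 × 0.421 = 0.58.
- One of 4: 0.5 + 0.25 × 0.421 = 0.61.

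The Hanley-McNeil standard error at an AUC of 0.60 is about 0.15 (5 v 15) to 0.17 (4 v 16). The bias of 0.08-0.11 is therefore under one standard error.

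**3. More than one affected draw.** Simulation (20,000 runs, 2 SD shift, two-sided t-test at 0.05):

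| Split | Failures affected | Mean AUC | Chance of p<0.05 |
|---|---|---|---|
| 5 v 15 | 1 | 0.58 | 8% |
| 5 v 15 | 2 | 0.67 | 24% |
| 5 v 15 | 3 | 0.75 | 49% |
| 4 v 16 | 1 | 0.60 | 10% |
| 4 v 16 | 2 | 0.71 | 32% |

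With the affected draws removed, AUC returns to 0.50 and the rate to about 5% (checked where at least two failures remain).

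**4. How many draws might be affected.** The documents do not say. Assume enzymes start to rise L = 7 to 14 days before biopsy and rejection is spread evenly over the 60 days after TAC stops. Of failures still in the study at a Visit 6 on day t, the share sampled inside that lead is L/(60 − t).

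- t = 15 (nominal): 7/45 to 14/45 = 16-31%, AUC 0.57-0.63. Since 45/60 = 75% of failures reach the visit (3 to 3.75 of 4-5), this is about 0.5 to 1.2 draws in all.
- t = 30: 7/30 to 14/30 = 23-47%, AUC 0.60-0.70. The window permits this: Visit 6 must be at least two weeks after Visit 5, and day 135 plus one month is day 165, which is 45 days after a day-120 Visit 5.
- All rejections on days 30-60 and Visit 6 on day 15: the earliest rejection is 15 days away, so with a lead of at most 14 days no draw is affected and the bias is nil.

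**The case against.** The omission is hard to dispute, but its importance is open to challenge.

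- **Size.** In the most plausible case about one draw is affected, the bias is smaller than the sampling error, and the chance of p<0.05 rises only from 5% to 8-10%. Lead time and rejection timing are assumptions, and one reading of the timing in Section 3 gives no effect. This stands.
- **Partial safeguards.** Blood at a biopsy concerning for rejection is a separate collection, and confirmed rejection ends participation. Section 3.3 already separates diagnostic from predictive markers at the time of rejection. The main flow-cytometry test uses the trajectory across visits, and no AUC specific to Visit 6 is named. This narrows the exposure to patients with rising enzymes who have not been biopsied, but nothing in the plan identifies them.
- **Signature content.** The earlier mRNA signatures separated rejection from other injury, so they are not pure injury markers. True, but a signature that detects rejection under way would be just as concurrent at Visit 6.
- **Pilot status.** A positive result leads to a funding request, not to clinical use. That limits the harm, yet choosing markers and time points is what the pilot is for.

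A reader might infer that an injury-following marker *would* be reported as predictive. The documents support only *could*: the outcome depends on how many failures are drawn late, which they do not state. A reader might also infer that a marker should count only if it separates the groups beyond ALT. That cannot be tested with 4-5 events, and it is partly circular because aminotransferases prompt the biopsy that defines failure.

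**Conclusion.** The point holds as a cheap improvement. As written, Visit 6 is the scheduled sample counted as predictive with no enzyme check behind it, and no planned analysis would show whether a signal there came before visible injury or accompanied it. Visit 4 is covered by the criteria check. So is Visit 5 in patients who go on to stop TAC, reading the Table 7-1 check as the continuation criteria.

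The size is unknown from the documents. With one affected failure and a 2 SD shift, mean AUC is 0.58-0.61 in place of 0.50. It is nil under late rejections with an on-time Visit 6, and 0.67-0.75 if two or three of five failures are affected. It would be wrong to conclude that the study's predictive results as a whole are invalid, since the pre-withdrawal comparisons do not share the problem.

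**What to change.** Add to Section 10.2:

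1. For each failure, list the days from each draw to biopsy and the same-draw AST/ALT, or the nearest values with their dates. The nearest value is needed as a fallback because Table 7-1 does not label Visit 6 a standard-of-care visit.
2. Flag Visit 6 draws, and Visit 5 draws in patients who do not stop TAC, when AST or ALT is at or above the existing two-fold limit in Section 5.2. Apply the flag to both outcome groups, for analysis only, and write down the reference value, which the criterion does not state. Report the Visit 6 comparison with and without flagged draws, and label the flagged ones concurrent/diagnostic. The biopsy prompt in Section 7.3 is a typical range and cannot serve as a cut-off. Rises below the flag remain visible in the listing.
3. Report the AUC of same-draw ALT descriptively beside each marker's AUC, in the same full set of patients. Do not compute it after removing flagged draws, which would truncate ALT.
4. Base any claim of prediction on pre-withdrawal samples and unflagged post-withdrawal samples. Set no requirement that a marker outperform ALT.

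Sections 4 and 7.4.4 should also be reconciled on how often liver tests are done, since this decides how close the nearest enzyme value will be.

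The cost is some wording and a little analysis on data already collected. About one failure draw may leave the restricted Visit 6 set, which makes a small group smaller. The unrestricted result is still reported.
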